1 INTRODUCTION

1.1 Overview

Coherus is developing CHS-1420 drug product (CHS-1420) as a proposed biosimilar to Humira® (adalimumab) under a global development strategy for chronic plaque psoriasis (PsO) and other indications for which Humira is approved in various regulatory territories.

CHS-1420 is being developed initially as a proposed biosimilar to Humira (US). Appropriate bridging studies (analytical, non-clinical, and clinical) will be performed that will allow filing of CHS-1420 as a proposed biosimilar to Humira sourced from the European Union, (EU) (Humira [EU]).

1.2 Background

The purposes of this study are to compare the efficacy and safety of biosimilar adalimumab (CHS-1420) developed by Coherus BioSciences, Inc. and an approved reference drug, Humira in subjects with chronic PsO and to compare the durability of responses to CHS-1420 and Humira.

Psoriasis is a chronic, autoimmune disease that appears on the skin. It occurs when the immune system sends out faulty signals that speed up the growth cycle of skin cells. Psoriasis is not contagious. There are 5 types of psoriasis. The most common form, PsO, appears as raised, red patches covered with a silvery white buildup of dead skin cells. Psoriasis can occur on any part of the body and is associated with other serious health conditions, such as arthritis, inflammatory bowel disease, diabetes, heart disease, and depression. Psoriasis is the most common autoimmune disease in the US. As many as 7.5 million Americans have psoriasis and 125 million people worldwide suffer with psoriasis ([National Psoriasis Foundation, 2014](#)).

Up to 30% of people with psoriasis also develop psoriatic arthritis (PsA), which causes pain, stiffness, and swelling in and around the joints. Psoriatic arthritis can develop at any time, but it most commonly appears between the ages of 30 and 50. Genes, the immune system, and environmental factors are all believed to play a role in the onset of the disease. Early recognition, diagnosis, and treatment of PsA are critical to relieve pain and inflammation and help prevent progressive joint damage.

Tumor necrosis factor (TNF) is a naturally occurring cytokine that plays an important role in the inflammatory processes of immune-mediated inflammatory diseases (IMIDs) such as PsO, PsA, juvenile idiopathic arthritis (JIA), polyarticular JIA, enthesitis-related arthritis, axial spondyloarthritis, ankylosing spondylitis (AS), axial spondyloarthritis without radiographic evidence of AS, psoriasis, Crohn's disease (CD), ulcerative colitis (UC), and rheumatoid arthritis (RA). Elevated levels of TNF are found in involved tissues and fluids of subjects with PsO and other IMIDs (Kruege, Krane, Carter, & Gottlieb, 1990) (Brotas, Cunha, Lago, Machado, & Carneir, 2012) (Keystone & Ware, 2010). Two distinct tumor necrosis factor receptors (TNFRs), a 55 kilodalton protein and a 75 kilodalton protein (p75), exist naturally as monomeric molecules on cell surfaces and in soluble forms. Biological activity of TNF is dependent upon binding to either cell surface TNFR. Accumulating evidence suggests differential effects of p75 TNFR in the pathogenesis of inflammatory and autoimmune disorders (Bluml, Scheinecker, Smolen, & Redlich, 2012). In addition to soluble tumor necrosis factor alpha (TNF α), its precursor form, transmembrane tumor necrosis factor alpha (mTNF α), is involved in the inflammatory response (Horiuchi, Mitoma, Harashima, Tsukamoto, & Shimoda, 2010).

Adalimumab inhibits binding of TNF α , but not tumor necrosis factor beta (TNF β), to cell surface tumor necrosis factor receptors TNFRs, rendering TNF α biologically inactive.

Humira was approved by the United States Food and Drug Administration (FDA) in 2002 for RA. Humira is indicated for reducing signs and symptoms, inducing major clinical response, inhibiting the progression of structural damage, and improving physical function in adult patients with moderate to severe active RA. Humira can be used alone or in combination with methotrexate or other non-biologic disease modifying anti-rheumatic drugs (DMARDs). Subsequently Humira has been approved for PsA, AS, JIA, PsO, CD, and UC (AbbVie US, 2014) as follows:

- PsA: Humira is indicated for reducing signs and symptoms, inhibiting the progression of structural damage, and improving physical function in adult patients with active PsA. Humira can be used alone or in combination with non-biologic DMARDs.
- AS: Humira is indicated for reducing signs and symptoms in adult patients with active AS.
- JIA: Humira is indicated for reducing signs and symptoms of moderately to severely active polyarticular JIA in pediatric patients 2 years of age and older. Humira can be used alone or in combination with methotrexate.

- PsO: Humira is indicated for the treatment of adult patients with moderate-to-severe chronic PsO who are candidates for systemic therapy or phototherapy, and when other systemic therapies are medically less appropriate. Humira should only be administered to patients who will be closely monitored and have regular Follow-up visits with a physician.
- CD: Humira is indicated for reducing signs and symptoms and inducing and maintaining clinical remission in adult patients with moderately to severely active CD who have had an inadequate response to conventional therapy. Humira is indicated for reducing signs and symptoms and inducing clinical remission in these patients if they have also lost response to or are intolerant to infliximab. Humira is also indicated for reducing signs and symptoms and inducing and maintaining clinical remission in patients 6 years of age and older with moderately to severely active Crohn's disease who have had an inadequate response to corticosteroids or immunomodulators such as azathioprine, 6-mercaptopurine, or methotrexate.
- UC: Humira is indicated for inducing and sustaining clinical remission in adult patients with moderately to severely active UC who have had an inadequate response to immunosuppressants such as corticosteroids, azathioprine, or 6-mercaptopurine. The effectiveness of Humira has not been established in patients who have lost response to or were intolerant to TNF blockers.

The recommended dosage of Humira for subjects with moderate to severe chronic PsO is 80 mg by subcutaneous (SC) injection followed by 40 mg by SC injection every other week (QOW). The most common adverse events (AEs) reported in clinical studies with adalimumab were injection site reactions (ISRs), infections, headache, and rash. Because the needle guards for both Humira and CHS-1420 contain latex, subjects with allergies to latex should not be enrolled in the study. Further details are provided in the prescribing information for Humira ([Appendix A](#)).

1.3 Development of CHS-1420

Unlike generic drugs, which are relatively simple chemical structures, biologic drugs are manufactured in cultured cells and vary lot to lot depending on the culture conditions. Because of these variations, biologic drugs cannot be considered “identical,” but may be considered “biosimilar.” Determination of biosimilarity is akin to determining the similarity of identical twins. Whereas identical twins are genetically identical, there may be minor differences in appearance, such as height or weight, which would allow them to be identified as unique and separate but biosimilar.

In order to be considered biosimilar, 2 biologics must meet the following criteria:

- Identical primary structures (i.e., amino acid sequence, and disulfide bonding)
- Highly similar post translational modifications (e.g., glycosylation)
- Highly similar 3-dimensional structures (e.g., α helix, β -sheet)
- Similar purity profiles
- Similar nonclinical in vitro pharmacology and in vivo pharmacokinetics (PK), toxicokinetics, and toxicity
- Similar responses in clinical trials including PK, safety, immunogenicity, and efficacy

See the Investigator's Brochure for more details.

2 STUDY OBJECTIVES

The primary objective of this study is to compare the efficacy (measured by the Psoriasis Area and Severity Index [PASI]) and safety of CHS-1420 and Humira at 12 weeks in subjects with moderate to severe chronic PsO. The secondary objectives are to compare the safety of and response to CHS-1420 over 24 weeks as well as efficacy/safety of switching from Humira to CHS-1420. Long term safety and efficacy of CHS-1420 during the open label extension over a further 24 weeks (Treatment Period 3) will be assessed.

3 INVESTIGATIONAL PLAN

3.1 Overall Study Design and Plan

This is a 48 week study with a follow up visit 8 weeks after the last dose, randomized, double-blind, active-control followed by open label safety, parallel group, multicenter, study in subjects with active, moderate to severe, chronic PsO. Approximately 500 subjects will be randomized at approximately 160 sites worldwide.

The study will consist of 23 weeks of administration of blinded study drug over a 24 week period, divided into Treatment Period 1 (16 weeks) and Treatment Period 2 (8 weeks), 23 weeks of open label CHS-1420 during 24 weeks of Treatment Period 3 and a Follow-up visit 56 days (8 weeks) after the last dose of study drug. Subjects who meet inclusion/exclusion criteria will be stratified by body mass index (BMI) < 30 kg/m² or ≥ 30 kg/m² and by age < 65 years or ≥ 65 years. Within these strata, subjects will be randomized to receive either CHS-1420 or Humira. Half of the subjects assigned to Humira will be assigned to receive CHS-1420 in Treatment Period 2 with the remainder continuing on Humira. For simplicity, the assignments for Treatment Period 1 and Treatment Period 2 will be made at the beginning of Treatment Period 1.

In Treatment Period 1, subjects will receive 2 subcutaneous (SC) injections of study drug on Week 0/Day 0 followed by single SC injections of study drug every other week (QOW) from Week 1/Day 7 through Week 15/Day 105.

For Treatment Period 2, subjects will: 1) continue on CHS-1420 or 2) Humira or 3) will be switched from Humira to CHS-1420 and they will continue to receive single SC injections of study drug QOW from Week 17/Day 119 through Week 23/Day 161.

For Treatment Period 3, all subjects that complete Treatment Periods 1 and 2 and achieve at least a 50% improvement in PASI score (PASI-50) at Week 24 will receive 23 weeks of open-label CHS-1420 in Treatment Period 3 QOW from Week 25/Day 185 through Week 47/Day 329.

The first dose of study drug on Week 0/Day 0 will be self-administered or administered by a caregiver at the investigative site, and subjects will be monitored for adverse reactions and ISRs during the 2 hours after this dose. Subsequent doses will be self-administered or administered by a caregiver at home. Subjects/caregivers will be trained on injection techniques and the electronic diary (eDiary) used to track compliance and subject-reported ISRs. Subjects/caregivers will contact the eDiary following each injection to document dosing on the day of injection and any possible ISRs after the injection.

The primary efficacy endpoint is the proportion of subjects achieving 75% improvement in Psoriasis Area and Severity Index (PASI-75) at Week 12. When an adequate amount of data are available for the primary endpoint, an independent, unblinded Data Monitoring Committee (DMC) will review the accumulating safety and efficacy to determine if the data are adequate to warrant continuing the study.

Subjects who discontinue study drug for any reason during Treatment Period 1 will be encouraged to return for all study visits through Week 16 and for the ET visit 56 days (8 weeks) after the last dose per the protocol Schedule of Procedures, and subjects who discontinue study drug for any reason during Treatment Period 2 or 3 will be encouraged to return for a Follow-up or ET visit 56 days (8 weeks) after the last dose of study drug (also per the protocol Schedule of Procedures). This Follow-up or ET visit will include evaluation of safety and immunogenicity (formation of anti-drug antibodies [ADAs]).

3.2 Rationale for Study Design/Dose Level

No clinical trials to evaluate the efficacy and safety of CHS-1420 in subjects with PsO have been performed to date. The design of this study is based on 2 clinical studies comparing adalimumab 80 mg ×1 followed by 40 mg QOW to placebo in subjects with moderate to severe psoriasis ([Menter, et al., 2008](#)), ([Gordon, et al., 2006](#)).

In a 52-week, randomized, double-blind, placebo-controlled, multicenter study, 1212 subjects with moderate or severe psoriasis were randomized 2:1 to receive either adalimumab or placebo at an initial dose of 80 mg followed by 40 mg QOW for the first 15 weeks ([Menter, et al., 2008](#)). Main exclusion criteria included exposure to anti-TNF therapy, other skin disease or infection that could interfere with evaluation, allergy to adalimumab or its constituents, current oral or injectable corticosteroid use, untreated tuberculosis (TB), poorly controlled medical conditions, history of neurologic symptoms suggestive of central nervous system demyelinating disease, and history of cancer or lymphoproliferative disease (other than successfully treated nonmelanoma skin cancer or localized carcinoma in situ of the cervix). Subjects achieving a PASI-75 response at Week 16 were eligible to continue in an open-label study and receive adalimumab 40 mg QOW for Weeks 17 through 31. Subjects who maintained a PASI-75 response at Week 33 were re-randomized to adalimumab or placebo QOW for an additional 19 weeks. The primary efficacy endpoints for this study were percentages of subjects achieving PASI-75 response at Week 16 relative to baseline and percentages of subjects losing adequate response after Week 33. At Week 16, 580/814 (71%) of adalimumab-treated versus 26/398 (7%) of placebo-treated subjects achieved at least PASI-75 scores. PASI-75 results at 12 weeks were also reported with 68% of subjects on Humira and 5% of subjects on placebo achieving PASI-75. The mean % change in PASI at 12 weeks for Humira was 76 compared to 15 for placebo. From Week 33 to Week 52, 5% of adalimumab-treated and 28% of placebo-treated subjects lost adequate responses.

In a 12-week, double-blind, placebo-controlled, multicenter study, 147 subjects with moderate to severe psoriasis were randomized to receive either an initial dose of 80 mg adalimumab followed by 40 mg adalimumab QOW, every week, or placebo ([Gordon, et al., 2006](#)). Subjects who completed the initial 12-week trial were eligible to continue in a 48-week extension trial. The primary efficacy analysis was the percentages of subjects achieving at least PASI-75 relative to baseline at Week 12 (for the initial trial) and at Week 24 (for the extension trial).

At 12 weeks, 53% of subjects receiving adalimumab QOW and 80% of subjects receiving adalimumab every week achieved PASI-75 compared to 4% of subjects receiving placebo (P<0.001).

Menter (Menter, et al., 2008) and Gordon (Gordon, et al., 2006) used the PASI-75 as the primary outcome measure with the PASI-75 evaluated at 16 weeks and 12 weeks, respectively. Both studies reported mean % change in PASI at Week 12: 76% Humira vs. 15% Placebo and 70% Humira vs. 14% placebo for Menter, 2008 and Gordon, 2006, respectively.

In this study (CHS-1420-02), eligible subjects are those who have a diagnosis of chronic PsO for at least 6 months that is moderate to severe as defined by a PASI score of greater than or equal to 12, Physician's Static Global Assessment (PSGA) score of greater than or equal to 3 (based on a scale of 0 to 5), and body surface area (BSA) affected by chronic PsO of greater than or equal to 10%. Subjects will be stratified by BMI < 30 kg/m² or ≥ 30 kg/m² and age < 65 years or ≥ 65 years (Menter, 2010).

The proposed dose level and dose regimen are consistent with that in the Humira (EU) Summary of Product Characteristics (AbbVie EU, 2014) and the Humira package insert (AbbVie US, 2014). In this study, 2 SC injections (2 pre-filled syringes, [80 mg]) of study drug will be administered on Week 0/Day 0. From Week 1/Day 7 through up to Week 23/Day 161, 1 SC injection (1 pre-filled syringe [40 mg]) of study drug will be administered QOW.

3.3 Selection of Study Population

3.3.1 Inclusion Criteria

Subjects must meet the following criteria to be enrolled in this study:

1. Male or female adult at least 18 years of age;
2. Diagnosis of chronic plaque-type psoriasis at least 6 months prior to Screening;
3. Moderate to severe chronic plaque type psoriasis as defined at Screening by:
 - a) PASI score of greater than or equal to 12,
 - b) PSGA score greater than or equal to 3 (based on a scale of 0 to 5), and
 - c) BSA affected by chronic plaque-type psoriasis of greater than or equal to 10%;
4. Considered a candidate by the Investigator to start Anti-TNF therapy for PsO;
5. ~~Anti-TNF therapy naïve;~~ (Deleted due to duplication with Exclusion Criteria #2)
6. ~~The patient has completed washout period prior to randomization for current or recent psoriasis therapies:~~
 - a. ~~2 weeks for disallowed topical therapies (see Section 4.8)~~
 - b. ~~4 weeks for ultraviolet B phototherapy~~

- e. 4 weeks for psoralen plus ultraviolet A phototherapy; phosphodiesterase type 4 (PDE4) inhibitors (e.g., apremilast)
- d. 12 weeks or a period equal to 5 times the half life of the biologic (other than anti-TNF) or investigational agent (whichever is longer) for other biologics or experimental therapies

Deleted Due to duplication with Inclusion Criteria #8 and #9 and Exclusion Criteria #4.

7. Able and willing to give written informed consent prior to performance of any study-related procedures; and
8. The patient has discontinued the use of any biologics or prohibited treatments as listed in [Section 4.8](#) (e.g., systemic corticosteroids, ultraviolet (UV), laser treatments, apremilast [Otezla], other phosphodiesterase type 4 [PDE4] inhibitors and kinase inhibitors) within the 28 days prior to Randomization (Week 0/Day 0);
9. The patient has stopped the use of American Dermatology Association class 1 to 5 topical corticosteroids ([Section 4.8](#)) within 15 days prior to Randomization (Week 0/Day 0).
10. ~~Able and willing to give written informed consent prior to performance of any study-related procedures; and~~ (Deleted due to duplication with Inclusion Criteria #7)
11. Women who meet one of the following:
 - a) Women of childbearing potential with a negative urine pregnancy test at Screening who agree to use 1 or more approved methods of birth control during the study. Approved methods of birth control are: hormonal contraception, intrauterine device, diaphragm plus spermicide, condom plus spermicide. Abstinence from heterosexual intercourse will be acceptable only if it is the preferred and usual lifestyle of the subject regardless of study participation; abstinence should be practiced for the duration of the study and until 5 months after taking the last dose of study drug; or
 - b) Women who have been postmenopausal for at least 2 years (with amenorrhea for at least 1 year/12 consecutive months) or have had a hysterectomy, bilateral salpingo-oophorectomy, or tubal ligation prior to signing the informed consent form (ICF).

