	
injection technique before administering study drug and on an electronic diary (eDiary), to track compliance and subject-reported ISRs. Subjects/caregivers will contact the eDiary following each injection to document dosing on the day of injection and any possible ISRs after the injection. During site visits, subject questionnaires will be completed by subjects using an electronic diary in the clinic.
 
The primary efficacy endpoint is the proportion of subjects achieving 75% improvement in Psoriasis Area and Severity Index (PASI-75) at week 12. The proportion of subjects achieving PASI-75 at 16 weeks will be a secondary efficacy endpoint.
 
An independent, unblinded Data Monitoring Committee will review Treatment Period 1 study data to determine if there is adequate safety and efficacy to warrant continuing the study to completion.
 
Subjects who discontinue study drug for any reason during Treatment Period 1 will be encouraged to return for all study visits through Week 16 if applicable and for the ET visit 56 days (8 weeks) after the last dose of study drug per the protocol Schedule of Procedures. Subjects who discontinue study drug for any reason during Treatment Period 2 or 3 will be encouraged to return for the Follow-up or ET visit 56 days (8 weeks) after the last dose of study drug (also per the protocol Schedule of Procedures). The Follow-up or ET visit will include evaluation of safety and immunogenicity (formation of anti-drug antibodies [ADAs]).

Study Centers	Approximately 160 active clinical sites worldwide will participate in this clinical trial.
Sample Size	The sample size determination is based on demonstrating a comparable PASI-75 at Week 12. Assuming that 70% of subjects in both the reference group, Humira, and the CHS-1420 group achieve PASI-75, with a statistical margin of 15% (absolute), approximately 250 subjects per treatment group will produce 90% power to establish equivalence at the 5% alpha level (2-sided) for the period 1 comparison. Subjects who lack follow-up data for the week 12 assessment will be considered non-responders in the primary analyses.
Study Population	Adult male and female subjects with moderate to severe chronic PsO.

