3.3.3 Completed Subjects

Subjects may be considered completers if the subjects complete 48 weeks of treatment and the Follow-up visit 8 weeks following the last dose in this trial (completes the study).

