- For subjects with PsA, administer HAQ-DI;
- Assess and record AEs;
- Perform study drug accountability; and
- Review subject's eDiary for any issues with compliance or with injecting study drug.

5.2.5 Follow-up or ET Visit (56 Days [8 weeks] After the Last Dose of Study Drug

The study will conclude when the last subject completes evaluations at the Follow-up visit or ET visit 56 days (8 weeks) after the last dose of study drug.

Subjects who complete Week 48/Day 336 efficacy and safety evaluations will be seen for a Follow-up visit 8 weeks after their last scheduled dose of study drug; subjects who discontinue the study prior to Week 48 will be seen for an ET visit 8 weeks/56 days after the last dose of study drug.

8 Weeks/56 days after the subject's last dose of study drug:

- Perform abbreviated physical examination and injection site assessments of all previous injection sites. The ISRs observed during examination of injection sites should be recorded as AEs. The AE term "ISR" with grade of AE consistent with the worst grade for any 1 of the characteristics of the ISR (pain, swelling, erythema, etc.) should be reported;
- Obtain vital signs (note: arm or wrist cuff for blood pressure and oral, aural, or axillary thermometer for temperature are acceptable)

- For Early Termination Subjects: obtain the following if not obtained within 4 weeks of the visit:
 - Blood samples for chemistry and hematology testing, and urine sample for urinalysis (and results were within the normal reference range for the test or within the specified allowed range for the protocol, e.g., liver function test results within $2 \times \text{ULN}$);
 - Perform 12-lead ECG
 - Weight;
- For Early Termination Subjects: obtain the following if not completed at the Week 12 or 16 visit (for subjects discontinuing study participation during Treatment Period 1) or at the Week 24 visit (for subjects discontinuing study participation during Treatment Period 2)
 - Obtain blood sample for hs-CRP for subjects with PsA
 - Perform PASI assessment;
 - Administer HAQ-DI for subjects with PsA;
 - Administer DLQI;
 - Administer EQ-5D;
- Perform PSGA (before SGA);
- Perform SGA of psoriasis;
- Collect serum sample for ADA testing;
- Collect serum sample for retention;
- Obtain blood sample for QuantiFERON-TB Gold test if this test has not been drawn and reported in last 3 months;
- Perform a urine pregnancy test for women of childbearing potential;
- Assess and record AEs;

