- Record concomitant medications;
- Perform study drug accountability for subjects discontinuing study participation early;
- Review subject's eDiary for any issues with compliance or with injecting study drug for subjects discontinuing study participation early;
- Collect any used and unused study drug if not previously collected, and assess compliance; and
- Contact IxRS to report subject's completion/discontinuation from study.

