11.1.2 Ethics Approval

It is the responsibility of the Investigator to ensure that the appropriate IRB or EC has reviewed and approved this protocol prior to initiating the study.

The IRB/EC must also review and approve the investigative site's ICF, other written information provided to the subject, and all advertisements that may be used for subject recruitment.

If the protocol or the ICF are amended during the study, the Investigator is responsible for ensuring that the IRB/EC has reviewed and approved these amended documents. In addition, IRB/EC approval of the amended documents must be obtained before implementation and before new subjects are consented to participate in the study using the amended version of the ICF. The Investigator must provide the CRA with the dated IRB/EC approval of the amended documents as soon as it is available.

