11.1.3 Subject Informed Consent

Prior to study entry, the Investigator, or a qualified person designated by the Investigator, will explain the nature, purpose, benefits, and risks of participation in the study to each subject, subject's legally acceptable representative, or impartial witness. Written informed consent must be obtained prior to the subject entering the study (before initiation of any study-related procedure and administration of the study medication). Sufficient time will be allowed to discuss any questions raised by the subject. If the consenting process is conducted by an Investigator designee, then the subject is offered the opportunity to discuss any of his/her questions or concerns regarding the ICF or the study with an Investigator. The Investigator or designated staff will document this process in the subject's medical record. An ICF must be signed by all subjects. The process of obtaining informed consent will be in compliance with all federal regulations, ICH GCP, and local laws.

If the ICF is amended during the study, the Investigator must follow all applicable regulatory requirements pertaining to approval of the amended ICF by the IRB/EC. The investigative site must use the amended ICF for all new subjects and repeat the consent process with the amended ICF for any ongoing subjects, as applicable.

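### Criterion 11a sets two post-dose contraception periods by method alone: 5 months for abstinence, but only to study end (56 days for a completer) for the listed methods

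*Combined protocol and SAP*

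**What the plan says.** Criterion 11a appears in Section 3.3.1 and, in the same terms, in the Synopsis. It admits women of childbearing potential with a negative urine pregnancy test "who agree to use 1 or more approved methods of birth control during the study". The approved methods are hormonal methods, an intrauterine device, and a diaphragm or a condom with spermicide. Abstinence is accepted only if it is the woman's usual lifestyle, and then "abstinence should be practiced for the duration of the study and until 5 months after taking the last dose of study drug".

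Section 3.3.3 and the Synopsis (Study Duration) define a completer by 48 weeks of treatment and "the Follow-up visit 8 weeks following the last dose in this trial (completes the study"). Section 5.2.5 gives the site a closing task at that visit: "Contact IxRS to report subject's completion/discontinuation from study". A subject who stops before Week 48 "will be seen for an ET visit 8 weeks/56 days after the last dose of study drug".

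Section 7.2.10 schedules the last urine pregnancy test at the Follow-up or ET visit. It requires a pregnancy to be reported if it occurs during the study or within 56 days of the last dose.

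**The concern.** The need for contraception after the last dose depends on how long the drug matters to a pregnancy, not on how pregnancy is avoided. Yet the criterion ties its longer period to abstinence alone. A site applying the text would release a woman using a listed method at the end of her study, and hold an abstinent woman with the same last dose to a later date.

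One of the two rules is therefore hard to defend. If 5 months is the intended precaution, users of the four listed methods are not asked for it. If about 56 days is enough, abstinent women carry a longer restriction without a stated reason. At stake is a participant-safety instruction that approximately 160 sites (Section 3.1) would apply as written.

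**Working it through.** **Inputs**
- Last scheduled dose: Week 47/Day 329 (Section 4.1).
- Follow-up or ET visit: 56 days after the last dose (Section 5.2.5); Week 55 with a window of ±1 week (Table 3).
- Abstinence period: until 5 months after the last dose (criterion 11a).
- Assumption: the documents do not define a month in days. Five consecutive calendar months are 150 to 153 days.

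**Reproducing the plan's own figure.** 329 + 56 = Day 385, and 385 / 7 = Week 55. This agrees with Table 3.

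**Gap for a completer**
- Listed methods end: Day 385.
- Abstinence ends: 329 + 150 = Day 479 to 329 + 153 = Day 482.
- Gap: 150 − 56 = 94 to 153 − 56 = 97 days, or 94/7 = 13.4 to 97/7 = 13.9 weeks.
- With the visit window: 150 − 63 = 87 to 153 − 49 = 104 days.
- With the widest assumption, months of 28 to 31 days each: 140 − 56 = 84 to 155 − 56 = 99 days.

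**Early stoppers.** A woman stopping in Period 2 or 3 who attends the ET visit on schedule has the same 94 to 97 days. Period 1 stoppers "will be encouraged to return for all study visits through Week 16 if applicable". One whose last dose was Day 0 and who does return is covered for 112 days, so her gap is smaller: 150 − 112 = 38 to 153 − 112 = 41 days.

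**Does the phrase about the study already include the 5 months?** Three places say not.
1. Criterion 11a names the duration of the study and the 5 months as separate parts of the abstinence period. If the first contained the second, the second would add nothing.
2. The live-vaccine rule (exclusion criterion 18 and Section 4.8) covers the study plus 3 months after the last dose. Where this protocol wants a post-dose period, it writes one.
3. Section 3.3.3 treats the 8-week Follow-up visit as completing the study for the subject.

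**Which period is intended?** The 5-month figure stands only in the abstinence clause. Against it, the last pregnancy test, the pregnancy reporting window (Section 7.2.10) and the routine SAE reporting period (Section 7.1.4) all rest on 56 days. The documents do not settle the question.

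**The case against.** The strongest reply is that the protocol's post-dose pregnancy monitoring is built on 56 days, which matches the end of the listed methods. On that view the 5-month clause is the outlier, and the documents establish no shortfall for anyone. This stands as far as it goes: intention cannot be read from the text. It does not remove the inconsistency, because abstinent women would then be held to an unexplained longer rule.

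A second reply concerns when the study ends. Section 5.2.5 also says that the study concludes with the last subject's final visit. If that governs criterion 11a, women enrolled early are covered for longer, some perhaps past 5 months, and no single gap applies. The per-subject reading is the more natural one, given the definition of a completer. Neither reading gives users of the listed methods a fixed period counted from their own last dose.

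Third, the practical effect depends on material not available here: the consent form, the Investigator's Brochure and the prescribing information. What women are actually told cannot be checked. That limits the consequence that can be claimed, but a correct consent form would still disagree with the criterion.

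A reader might go further and infer that 56 days is too short, or that users of the listed methods lose about 63% of a needed precaution (94/150 = 62.7% to 97/153 = 63.4%). The documents do not support this. The percentage has meaning only if 5 months is the right length, and no source for 5 months is given.

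**Conclusion.** The inconsistency is real and the wording is current. Criterion 11a sets two post-dose periods by method alone, with no stated reason. For a completer they differ by about 94 to 97 days, assuming calendar months and a study end counted per subject; the visit window widens this to 87 to 104 days.

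The documents do not show that either period is the correct one, and no harm is demonstrated. The number of women affected cannot be stated, since there is no count of women of childbearing potential and no split by method. Sample size, the primary endpoint and the equivalence analysis are unaffected. This is an inexpensive improvement in participant safety. Confidence is high for the mismatch in wording, and lower for its practical effect.

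**What to change.** Amend criterion 11a in Section 3.3.1 and in the Synopsis so that every accepted method, abstinence included, applies throughout the study and up to 5 months from the last dose. Five months is the protective default because the protocol already states it; another single period is acceptable if the sponsor justifies it. Extend the pregnancy reporting window in Section 7.2.10 to the same period. Otherwise contraception would be required for about 94 to 97 days beyond the point at which a pregnancy must be reported. At the existing Follow-up/ET visit, remind women of childbearing potential of the period and ask them to report a pregnancy within it.

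The cost is one sentence in two places, a matching change in Section 7.2.10 and a reminder, with no added visit. Safety staff would have to accept pregnancy reports for about three months longer. It remains an amendment: under Section 11.1.2, "IRB/EC approval of the amended documents must be obtained before implementation and before new subjects are consented", and under Section 11.1.3 sites must "repeat the consent process with the amended ICF for any ongoing subjects, as applicable". It can travel with the next amendment. The main downside is a longer contraception commitment for users of the listed methods, including women already enrolled.
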